## Protocol Summary

Title	Open Label Multi-Center Study of Emergency Hyperbaric Oxygen for Respiratory Distress in Patients with COVID-19
Short Title	Hyperbaric Oxygen for COVID-19 Patients
Brief Summary	
This is a multi center prospective pilot cohort study to evaluate the safety and preliminary efficacy of hyperbaric oxygen therapy (HBOT) as an emergency investigational device for treating patients with respiratory distress due to a novel coronavirus disease, COVID-19. HBOT is a therapy that has been FDA approved for the treatment of decompression sickness, gas gangrene, late effects of radiation and others. HBOT is a medical intervention using a rigid chamber and compressed oxygen to treat hypoxia and modulate negative inflammatory responses. It has demonstrated a good safety profile and has been shown to blunt the damaging immune responses in animal models.
 
The mechanism of respiratory failure in COVID-19 is unknown but lung pathology demonstrates "edema, proteinaceous exudate, focal reactive hyperplasia of pneumocytes with patchy inflammatory cellular infiltration and multi nucleated giant cells. Fibroplastic plugs were also noted in airspaces." One potential mechanism is thought to be due to a cytokine storm from an overwhelming viral load. Hyperbaric Oxygen therapy has been shown to modulate the immune system in the laboratory rat model and is used to modulate the inflammatory response in reperfusion injury. We hypothesize that hyperbaric oxygen may be useful to modulate the immune response in COVID-19 infected patients and increase oxygenation. A recently non-peer reviewed study of hyperbaric oxygenation in Wuhan, China demonstrated that it was well-tolerated, safe with clinical improvement of oxygenation for all five patients that were enrolled.
 
In summary, HBOT treatment will be provided to patients as an adjunct to standard therapy for a cohort of 40 COVID19-positive patients with respiratory distress at NYU Winthrop Hospital. All patients prior to the clinical application of HBOT will be evaluated by the primary care team and hyperbaric physician. During the interim analysis of the first 10 patients and after the intervention portion of this study, a chart review will be performed to compare the outcomes of intervention patients versus age and gender matched control patients who received standard of care.

Phase	Emergency Investigational Device

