## 2 Introduction, Background Information and Scientific Rationale

### 2.1 *Background Information and Relevant Literature*

A novel coronavirus, similar to the one that caused severe acute respiratory syndrome (SARS) that began in Wuhan, China, is now a pandemic. With first cases confirmed in the United States nearly 4-6 weeks ago, we anticipate this spread will continue to increase before it plateaus or even decreases. It is highly contagious and is quickly evolving. The first cases were originally linked to animal-human transmission but has since then been transmitted from human-to-human at an exponential rate. Aerosol transmission through respiratory droplets from coughing or sneezing is another primary mechanism.

However, those individuals that are affected have presented in variable clinical presentations from asymptomatic to mild disease to extensive systemic immune reactions requiring mechanical ventilatory assistance. The pathogenic mechanism is still under research but seems complex. The viral infection amounts an excessive immune reaction within the host, activating leukocytes and interleukins that maintain a pro-inflammatory disease state.

Hospital staff, beds, and supplies are limited. The growing number of patients requiring supplemental oxygen and mechanical ventilation is increasing. There is an urgent need to capture this subset of COVID-19 patients prior to clinical respiratory deterioration.

Hyperbaric oxygen therapy (HBOT) presently has been trialed in Wuhan and Italy and has shown feasibility and safety. Hyperbaric oxygen provides patients with 100% inhaled oxygen at an increased atmospheric pressure and has been used as adjuvant therapy to decrease inflammatory states. It has been used in supportive therapy for refractory hypoxia, however, the efficacy of HBOT in treating severe hypoxia in patients with COVID-19 has not been evaluated. Due to the severity of this illness further treatment and studies are needed to begin as soon as possible.

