### 5.5 Use of DataCore/Epic Information for Recruitment Purposes

This study will utilize internal physician referral of patients that have tested positive for COVID-19 and are thought to benefit from HBOT and study enrollment. EPIC will be used to determine if subjects meet study eligibility criteria. Any recruitment information sent by email will utilize Send Safe email.

Once contact is made, approved recruitment language will be used to communicate the reason they are being contacted and subjects will be asked if they are interested in participating in this specific study. Should the potential subjects agree, the study team will provide the subjects with information regarding the next steps for participation.

If a subject requests information regarding opting out of further recruitment for all research, subjects will be directed to contact [[contact]](mailto:[contact]) or [name].

Epic will also be utilized to access deidentified data on patients who received standard treatment.

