## **5.7 Total Number of Participants and Sites**

There are a total number of 11 sites. All sites will submit their own individual IRB proposal to be approved by their respective institution's IRB. NYU is the lead site and the Co-Principal Investigators, [name] and [name], will be the lead coordinators of this study.

Recruitment will end when approximately 40 participants are enrolled in the HBOT group.

We will create a comparison cohort from chart review of 120 patients who received standard treatment and were matched with 40 HBOT patients in 3:1 ratio, such that the comparison group will consist of 120 standard of care patients. For this retrospective comparison group, we will be requesting a waiver of consent and authorization for this cohort.

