### 9.3 Analysis Datasets

We will compare study endpoints and safety outcomes between the 40 patients who received HBOT treatment with a matched comparison group of 120 patients who received standard treatment. Matching will be based on age, gender, comorbidity, and disease severity. The eligibility criteria for the SOC group will be consistent with that of the HBOT group.

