### 9.4 Description of Statistical Methods

#### 9.4.1 General Approach

We will summarize the continuous variables using mean, median, standard deviation and ranges, and the categorical variables using frequency and proportions. Variables will also be summarized graphically. Baseline characteristics of the participants who received HBOT will be compared with that of control patients receiving SOC. If we find any significant difference in the baseline variables between the two matched groups, we will adjust for them as covariates in outcome analysis. T-test or ANOVA will be used for continuous variables whereas chi-squared test will be used for comparison of proportions. All tests will be two tailed at significance level of 0.05. Appropriate transformations (such as log transformation) will be considered for any continuous variable that indicates non-normality. Statistical software R and SAS will be used for the analysis.

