### **9.5 Sample Size**

Using a sample of 160 patients, 40 in HBOT arm and 120 in SOC arm (post matching) we can detect a reduction of 22.5% or higher, against the null of no difference, with 80% power at significance level of 0.05, assuming that the mortality rate in SOC arm is about 80%.

For the secondary analysis, our proposed sample of 160 patients will similarly allow us to detect a difference of 22.5% in need for ventilation between HBOT group and SOC group with 80% power. For comparing the continuous outcome of number of days in ventilation, we have 80% power to detect effect size (cohen's d) of 0.51 with 160 patients.

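### Standard-of-care charts are not tied to the HBOT patient's hospital or calendar period, so site or period differences can imitate or hide an HBOT effect

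*Combined protocol and SAP*

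**What the plan says.** The primary comparison sets 40 HBOT patients against 120 chart-review patients, three per HBOT patient (sections 5.7 and 9.3). The matching rule appears in three forms:

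- Section 9.3: "Matching will be based on age, gender, comorbidity, and disease severity".
- Protocol Summary (Brief Summary) and section 4.1: age and gender only.
- Protocol Summary (Reference Therapy): age and gender, with comorbidity and initial severity where possible.

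None names hospital or date. Section 9.3 asks that controls meet eligibility criteria consistent with those of the HBOT group, again without a site or date condition.

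On sites, section 5.7 says "There are a total number of 11 sites", while the Brief Summary still describes treatment "for a cohort of 40 COVID19-positive patients with respiratory distress at NYU Winthrop Hospital". On the source of control data, section 5.5 says "Epic will also be utilized to access deidentified data on patients who received standard treatment" without saying whose system. On setting, section 2.1 describes a rapidly changing outbreak and adds "Hospital staff, beds, and supplies are limited".

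On analysis, section 9.4.2 uses a chi-squared test on the two pooled groups, followed by a logistic regression on covariates judged to be confounders. Section 9.4.1 adjusts for baseline variables that differ significantly. Section 9.1 leaves the formal SAP to the end of a non-blinded study.

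**The concern.** Without randomization (section 9.6.1), control selection is the main protection for the comparison of HBOT with standard of care. Matching on patient features balances those features. It does not balance where and when a patient was treated. If mortality or use of ventilation differs between hospitals or weeks, and the two groups are spread differently over them, the difference passes into the estimated HBOT effect. Both the primary endpoint and the first secondary endpoint are exposed, as is the interim comparison of 10 with 30 patients in section 9.4.7.

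The adjustment rule is a weak safeguard. It names neither site nor date, it depends on a baseline significance test or a later judgement, and it leaves the crude chi-squared test as the primary result. If controls come from hospitals that treat few HBOT patients, a regression has little within-site overlap to work with.

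**Working it through.** **Inputs.** Groups of 40 and 120 and standard-of-care mortality of about 80% (section 9.5). "All tests will be two tailed at significance level of 0.05" (section 9.4.1). Uncorrected chi-squared test (section 9.4.2 names no continuity correction). The documents give no site or period gap, so it is varied as an assumption.

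**Step 1: the plan's own figure.** Section 9.5 says "we can detect a reduction of 22.5% or higher, against the null of no difference", with 80% power. Read as an absolute difference, this is 0.80 against 0.575.

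- Pooled proportion: (120 × 0.80 + 40 × 0.575)/160 = 0.74375.
- SE under the null: √(0.74375 × 0.25625 × (1/120 + 1/40)) = 0.0797.
- SE under the alternative: √(0.80 × 0.20/120 + 0.575 × 0.425/40) = 0.0863.
- Power: Φ((0.225 − 1.96 × 0.0797)/0.0863) = Φ(0.797) = 78.7%. Exact enumeration of all outcomes gives 79.2%.

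The stated 80% is reproduced closely enough to use the same test below.

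**Step 2: no HBOT effect, net gap favouring the HBOT group.** For a 10-point gap (0.80 against 0.70), the pooled proportion is 124/160 = 0.775 and the two SEs are 0.0762 and 0.0811. Φ((0.10 − 1.96 × 0.0762)/0.0811) = Φ(−0.609) = 27.1%. Exact enumeration, both tails:

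| Control mortality | 0 points | 5 points | 10 points | 15 points |
|---|---|---|---|---|
| 80% | 5.0% | 11.6% | 27.4% | 49.1% |
| 50% | 4.9% | 8.4% | 19.2% | 37.6% |
| 40% | 5.0% | 8.3% | 19.8% | 40.2% |
| 30% | 4.9% | 8.2% | 21.5% | 46.5% |

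**Step 3: the opposite direction.** Suppose HBOT truly lowers mortality by 22.5 points, but the HBOT patients' sites or weeks carry 5, 10 or 15 points more risk. Expected HBOT mortality becomes 0.625, 0.675 or 0.725 against 0.80. The same enumeration gives power of 60%, 38% and 18% in place of 79%.

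**Step 4: what produces such a gap.** With two strata (sites or periods), net gap = difference in mortality between strata × difference in the groups' shares of a stratum. Take mortality of 80% and 60%, controls split 90/30 and HBOT patients 10/30:

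- Controls: (90 × 0.80 + 30 × 0.60)/120 = 0.75.
- HBOT: (10 × 0.80 + 30 × 0.60)/40 = 0.65.
- Net gap: 10 points, which is 20 points × (0.75 − 0.25).

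With mortality of 85% and 55% and the same split, the gap is 30 × 0.50 = 15 points.

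**Step 5: does the remedy work?** Simulation of step 4 with no HBOT effect, 40,000 runs per case:

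| Strata | Crude chi-squared as planned | Cochran-Mantel-Haenszel, same controls | Crude test, controls matched 3:1 within stratum (30/90) |
|---|---|---|---|
| 80% / 60% | 24% | 5.0% | 4.7% |
| 85% / 55% | 47% | 4.8% | 4.3% |

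Matching within stratum brings the spurious benefit to about zero. In one matched example (control mortality 90% and 70%, true effect 22.5 points), power is 80% with the crude test and 81% with the stratified test. Where the control sets can be filled, the remedy need not raise the sample size.

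**The case against.** The strongest reply is that the consequence is possible, not shown. Bias needs outcomes to differ by site or week and the two groups to be distributed differently over them. Step 4 shows that a net gap of 10 points takes a large difference on both counts. The calendar range may also be short: section 2.1 puts the first US cases four to six weeks back, and the Summary plans about two months. The study calls itself a pilot. All of this stands, and it limits how firmly any size can be asserted. It does not supply the missing rule.

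Three stronger readings are tempting, and the documents do not support them.

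- A reader might infer that controls will come mostly from the lead institution or from earlier weeks. Section 5.5 does not say whose Epic is meant, section 13.1 gives data collection to staff at each site, and no section mentions earlier weeks. The Brief Summary's single-hospital wording concerns the HBOT cohort. If it governed, lead-institution controls would share that cohort's site.
- A reader might infer that the bias must favour HBOT. Nothing fixes its direction.
- A reader might infer that adjustment for site or date is ruled out. Sections 9.4.1 and 9.4.2 allow it, but do not require it.

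On the remedy, 40 patients over 11 sites is about 3.6 per site. Section 9.6.1 promises many eligible charts overall, not at each site. Full sets of three close matches may not always be found, so a rule for incomplete sets and an adjusted analysis are both needed.

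**Conclusion.** The point holds as a gap in the design. The matching rule, followed exactly in any of its three forms, permits controls from other hospitals and other weeks, and the primary test does nothing to separate those differences from treatment. At the plan's 80% control mortality, an assumed net gap of 5 to 15 points in HBOT's favour raises false-positive findings from 5% to between about 12% and 49%. A gap in the other direction costs power on a similar scale. Each of these gaps is smaller than the 22.5 points the study is sized to detect. That outcomes vary by hospital and week is a reasonable inference from section 2.1, not a statement in the protocol. The matter should be settled before controls are selected, because leaving it to a SAP written at the end of an open study means deciding once outcomes can be known.

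**What to change.** - **Control selection (sections 9.3 and 5.7).** Take each control from the same hospital as its HBOT patient, within a stated window around that patient's entry, for example 14 days. Define the control's date as the day the eligibility criteria were first met.
- **Incomplete sets.** Widen the window before crossing sites, or accept fewer than three controls.
- **Consistency.** Bring the matching text in section 4.1 and both places in the Protocol Summary into line with section 9.3, and reconcile the single-hospital wording with the list of 11 sites.
- **Analysis (section 9.4.2).** Before control outcomes are seen, pre-specify an analysis that accounts for site and calendar period whatever the baseline tests show, for example Cochran-Mantel-Haenszel or regression with those terms. This also covers imbalance left when windows widen or sites are crossed. With many small sites, state how sparse strata will be combined.
- **Reporting.** Show site and entry date by group. State as a limitation that selection into HBOT by referral and consent remains.

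The cost is a chart pull at each participating site, and looser comorbidity and severity matching or fewer controls at low-volume sites.

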### 9.4 Description of Statistical Methods

#### 9.4.1 General Approach

We will summarize the continuous variables using mean, median, standard deviation and ranges, and the categorical variables using frequency and proportions. Variables will also be summarized graphically. Baseline characteristics of the participants who received HBOT will be compared with that of control patients receiving SOC. If we find any significant difference in the baseline variables between the two matched groups, we will adjust for them as covariates in outcome analysis. T-test or ANOVA will be used for continuous variables whereas chi-squared test will be used for comparison of proportions. All tests will be two tailed at significance level of 0.05. Appropriate transformations (such as log transformation) will be considered for any continuous variable that indicates non-normality. Statistical software R and SAS will be used for the analysis.

#### 9.4.2 Analysis of the Primary Efficacy Endpoint(s)

The primary endpoint will be patient mortality, a binary outcome variable indicating whether a patient died during hospitalization for COVID treatment. We will compute proportion of patients who died in each

CONFIDENTIAL

This material is the property of the NYU School of Medicine and Langone Medical Center. Do not disclose or use except as authorized in writing by the study sponsor

matched group. Chi-squared test will be utilized to compare rates of incident mortality in each group. We will also report estimates of difference in proportions along with an estimate of uncertainty using 95% confidence interval.

As a follow-up analysis, we will use a multivariable logistic regression, adjusting for any baseline covariates determined to be confounder, to estimate odds-ratio of probability of mortality between HBOT group and SOC group. We will also report 95% confidence interval of the odds-ratio.

Sample size consideration: Using a sample of 160 patients, 40 in HBOT arm and 120 in SOC arm (post matching) we can detect a reduction of 22.5% with 80% power at significance level of 0.05, assuming that the proportion of mechanical ventilation needed in SOC arm is about 80%.

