Description of Study Agent/Procedure	
Hyperbaric oxygen therapy involves placing patients in an enclosed chamber with 100% inhaled oxygen at an increased atmospheric pressure. HBOT chambers have shown efficacy and been cleared by the FDA for 13 conditions:
 
 
• Air or gas embolism
 
• Carbon monoxide poisoning
 
• Clostridial myositis and myonecrosis (gas gangrene)
 
• Crush injury, compartment syndrome, and other acute traumatic ischemias
 
• Decompression sickness
 
• Enhancement of healing in conditions including:                     
 
◦ Diabetically derived illness, such as diabetic foot, diabetic retinopathy, diabetic nephropathy
 
◦ Exceptional blood loss (anemia)
 
◦ Intracranial abscess
 
◦ Necrotizing soft tissue infections (necrotizing fasciitis)
 
◦ Osteomyelitis (refractory)
 
◦ Delayed radiation injury (soft tissue and bony necrosis)
 
◦ Skin grafts and flaps (compromised)
 
◦ Thermal burns
 
 
 

Reference Therapy	
Standard of care matched cohort of patients that did not receive HBOT based on age and gender and if possible underlying medical comorbidities and initial disease severity.

Key Procedures	
 
• Hyperbaric Oxygen Treatment
 
• Review of standard of care pre and post treatment blood draws to evaluate the blood oximetry along with markers of inflammation (e.g., D-dimer, Lymphocytes, IL-6, Ferritin, LDH, CRP, ESR, Fibrinogen, and troponin)
 
• Chart review
 

Statistical Analysis	
For binary primary and secondary endpoints, chi-squared analysis of proportions between the two matched groups with multivariate logistic regression if we find identifiable differences in the two study arms. T-test and linear regression for secondary endpoints that are continuous variables.

CONFIDENTIAL

This material is the property of the NYU School of Medicine and Langone Medical Center. Do not disclose or use except as authorized in writing by the study sponsor

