#### **9.4.3 Analysis of the Secondary Endpoint(s)**

The first secondary endpoint is a binary outcome indicating whether a patient needed a mechanical ventilation. We will compute the proportion of patients who needed mechanical ventilation during their treatment for each matched group. The proportion in HBOT arm will be compared with that in matched SOC using chi-square test for proportions. Estimate of difference in proportion along with 95% confidence interval will be reported. Similar to the primary analysis, we will adjust for any potential confounders, deemed important in the baseline analysis, by using multivariable logistic regression. Estimate of odds-ratio and 95% confidence interval will be reported.

To compare the average number of days spent in ventilator between the two groups, we will use linear regression analysis. The distribution of outcome, the number of days in ventilator, will be assessed graphically and by conducting test for normality. If we find the evidence of deviation from normal distribution the outcome will be log transformed before proceeding with analysis. We will also adjust for any potential confounders, deemed important in the baseline analysis. Slope coefficient along with 95% confidence interval will be reported as an estimate of difference between HBOT and SOC groups.

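### The leading mortality result in this non-randomised comparison is unadjusted; the adjusted estimate is a follow-up with no covariate named, and its only stated trigger misses most moderate imbalances

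*Combined protocol and SAP*

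**What the plan says.** Section 9.6.1 rules out randomisation. Section 5.5 recruits by physician referral of patients expected to benefit, and Section 5.7 draws 120 controls from chart review at 3:1.

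For mortality, Section 9.4.2 states: "Chi-squared test will be utilized to compare rates of incident mortality in each group". A raw difference in proportions with a 95% interval goes with it. Then: "As a follow-up analysis, we will use a multivariable logistic regression, adjusting for any baseline covariates determined to be confounder". No covariate is listed.

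The rule for adjusting is worded in four ways:
- Protocol Summary, statistical analysis row: "multivariate logistic regression if we find identifiable differences in the two study arms".
- Section 9.4.1: "If we find any significant difference in the baseline variables between the two matched groups, we will adjust for them".
- Section 9.4.2: covariates judged to be confounders, with no criterion.
- Section 9.4.3 (secondary endpoints, described as similar to the primary analysis): "any potential confounders, deemed important in the baseline analysis".

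The matching rule also varies. Section 9.3 commits to age, gender, comorbidity and severity, with eligibility consistent across groups. The reference-therapy row of the Protocol Summary gives age and gender and then "if possible underlying medical comorbidities and initial disease severity". The brief summary and Section 4.1 mention only age and gender. No severity measure is defined.

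Section 9.1 leaves the formal SAP to the end of a non-blinded study. Section 9.4.7 compares all endpoints for the first 10 HBOT patients with 30 matched controls before then.

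**The concern.** Without randomisation, confounding by severity is the main threat to the mortality comparison. An unadjusted risk difference carries any severity imbalance left after matching straight into the estimate and its interval. If HBOT patients were the less severe group, that would look like benefit. The adjusted analysis meant to deal with this ranks second and has no fixed content. The one operational criterion for adjusting is a significance test, which reflects the size of the groups as much as the size of the imbalance. With the covariates open and the SAP written last, the choice of model can be made after outcomes are known.

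**Working it through.** **1. Which analysis the plan's power belongs to.** Section 9.5 claims 80% power for a 22.5% reduction with 40 v 120, "assuming that the mortality rate in SOC arm is about 80" per cent. Taking this as 80% v 57.5%, two-sided 0.05, pooled test:
- pooled proportion = (40 × 0.575 + 120 × 0.80)/160 = 0.744
- null SE = √[0.744 × 0.256 × (1/40 + 1/120)] = 0.0797
- alternative SE = √[0.575 × 0.425/40 + 0.80 × 0.20/120] = 0.0863
- power = Φ[(0.225 − 1.96 × 0.0797)/0.0863] = Φ(0.797) = 78.7% (79.2% by exact enumeration).

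The claim is reproduced to within about a point, for an unadjusted two-proportion test and an absolute difference. A relative reading (80% to 62%) gives 62.1%. The design was therefore sized on the chi-squared test. Section 9.4.2 attaches the same rate to a different endpoint, "assuming that the proportion of mechanical ventilation needed in SOC arm is about 80" per cent, so I use a range of mortality rates below.

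**2. Sensitivity of the Section 9.4.1 trigger.** For a continuous severity measure in SD units:
- SE of the difference = √(1/40 + 1/120) = 0.1826
- difference needed = t(0.975, 158 df) × 0.1826 = 1.975 × 0.1826 = 0.361 SD
- chance of being flagged, from the noncentral t distribution: 8.5% at a true 0.10 SD, 19.3% at 0.20 SD, 37.2% at 0.30 SD.

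A true imbalance of 0.30 SD therefore goes unflagged in about 63% of studies.

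**3. Bias in the raw risk difference.** Assumptions not in the documents: no HBOT effect; severity normal with SD 1; HBOT mean lower by d; odds ratio for death 2 or 3 per SD. With expit the inverse logit, intercept a and slope b = ln(OR), choose a so that E[expit(a + bZ)] equals SOC mortality for Z ~ N(0,1). Bias = that mortality − E[expit(a + b(Z − d))]. Results in percentage points, OR 2 / OR 3:

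| SOC mortality | d = 0.10 SD | d = 0.30 SD |
|---|---|---|
| 80% | 1.05 / 1.52 | 3.26 / 4.78 |
| 50% | 1.56 / 2.20 | 4.68 / 6.57 |
| 30% | 1.31 / 1.86 | 3.84 / 5.38 |
| 10% | 0.58 / 0.85 | 1.66 / 2.37 |

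I take 0.10 SD to stand for the four-factor matching working, and 0.30 SD for severity not being matched. At 80% mortality the second case is 3.26/22.5 = 14% to 4.78/22.5 = 21% of the design difference.

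**4. Effect on the test.** Simulated with no HBOT effect, 80% mortality and the same assumed severity effects:
- At 0.10 SD, the two-sided chi-squared false-positive rate is 4.1% to 5.9%, close to nominal.
- At 0.30 SD, chi-squared rejects in HBOT's favour roughly 6% to 10% of the time, against a nominal 2.5%. A model containing severity does so about 2% to 3% of the time. The chi-squared figure moves by a point or two with how sets and severity are modelled.

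**5. What adjustment can and cannot do.** At 0.30 SD and 80% mortality, with age, sex and comorbidity in the outcome model, the raw bias is 2.97 / 4.41 points (OR 2 / OR 3). Adjusting for severity measured with reliability 0.8 leaves 0.59 / 0.86 points, and with reliability 0.6 leaves 1.19 / 1.74 (reliabilities assumed). So 60% to 80% of the bias is removed. Dropping patients with a missing covariate is costly: simulated adjusted power at the 22.5-point difference falls from about 80% to 73% with 20% of patients incomplete, and to 65% with 30% (missing rates assumed).

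**The case against.** **Adjustment and matching are already planned.** Section 9.4.2 commits to an adjusted odds ratio with an interval, Section 9.4.1 to adjusting for significant differences, and Section 9.3 to matching on four factors. This stands: a reader might infer that mortality will be reported only unadjusted, and the text does not support that. What remains is the adjusted result's lower rank and unnamed content, and a matching rule that the summary and Section 4.1 weaken.

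**The hierarchy can be inferred.** The follow-up label, the hypothesis of equal proportions in Section 9.2 and the power calculation all point to chi-squared. This also stands. No sentence says what happens if the two results disagree, but it would go too far to say that the plan gives no indication of which leads. The complaint is that the one which leads is unadjusted.

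**The harm is assumed.** Imbalance, severity effect and direction all come from outside the documents. Referral of patients expected to benefit does not say whether they are sicker or less sick, so the bias could hide a benefit as easily as create one. With effective severity matching it is 1.0 to 1.5 points at 80% mortality. All of this stands, and it limits the size of the point. The 8%, 19% and 37% apply to the Section 9.4.1 wording only; the other wordings could be applied more generously, but they give no criterion.

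**It is a pilot.** That moderates the point, but Sections 9.2, 9.4.1 and 9.5 still set a mortality hypothesis, a significance level and power.

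**The interim statistician is blinded (9.4.7.2).** This covers the interim analysis and does not fix the final covariates.

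**Conclusion.** The point holds as a weakness that should be fixed. In a non-randomised comparison the leading mortality estimate should not be the raw one, with adjustment left to a trigger that misses a 0.30 SD imbalance in about 63% of studies. That much rests on the text and on the 40 v 120 split alone.

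The size is conditional. At 80% mortality it is a small bias if Section 9.3's matching is carried out, and up to about a fifth of the design difference if severity is left unmatched. Across the mortality rates examined, the 0.30 SD bias runs from 1.7 to 6.6 points.

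Two stronger readings are not supported. A reader might infer that the chi-squared test has a seriously inflated error rate in any case; with severity matched it stays near 5%. A reader might also infer that adjusting would raise power; that cannot be claimed, because Section 7.1.2 collects chart items only where they were done as standard of care.

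The SpO2 criterion is a separate conflict: one row of the Protocol Summary measures it after a non-rebreather trial, while another row and Section 5.1 use room air. Those passages must be reconciled.

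**What to change.** 1. **Governing result (9.4.2).** Use a prespecified logistic model with treatment, age, sex, comorbidity and one defined baseline severity measure recorded the same way in both groups, all included whatever the baseline p-values. Report the standardised risk difference with 95% CI. State the scale of the test, and account for matched sets if they are formed. Keep chi-squared and the raw difference as supportive. Put this one rule in place of the wordings in the Protocol Summary, 9.4.1 and 9.4.3.
2. **Missing covariates.** Prespecify a rule that keeps every patient in the model, for example multiple imputation, and make no claim of a power gain.
3. **Sparse outcomes.** Prespecify a simpler treatment-plus-severity model, or linear regression as a sensitivity analysis, for few deaths or few survivors. Fix any threshold in advance on pooled counts and check how often it would apply. A cut at fewer than 25 pooled deaths or survivors, for instance, would be reached 6.6% of the time at 80% mortality but 55% of the time at 85% or 15%.
4. **Matching.** Bring the brief summary, the reference-therapy row and Section 4.1 into line with the four factors in 9.3. Judge balance by standardised differences rather than p-values.
5. **Timing.** Settle these rules, and select controls without sight of outcomes, before the interim chart review in 9.4.7 instead of in an end-of-study SAP.

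Cost: protocol and SAP wording and some analysis work, with no extra patients. The result will depend on how complete the charts are. Adjustment reduces confounding by referral but does not remove it.
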